5.2 EFFECTIVENESS: MEAN PERCENT ECC CHANGE PREOPERATIVELY VS. POSTOPERATIVELY

The mean percent change in ECC from preoperative to 3 months postoperative will be reported by descriptive statistics for both OVD groups for safety population, PP population and sensitivity analysis. For ITT (with imputation), only the mean difference between the two OVD groups will be reported. The percent change in ECC from preoperative to postoperative is calculated as followed:

$$\text{Percent change in ECC} = (\text{Postop ECC} - \text{Preop ECC}) / \text{Preop ECC}$$

The difference in mean percent change in ECC will be analyzed by a paired t-test. The hypothesis testing of non-inferiority for mean percent ECC change will be tested using a 1-sided, paired t-test at an alpha of 0.025 and a delta of 5%. The null hypothesis is that the paired mean difference for mean percent change in ECC is equal to or less than -5%. The alternative hypothesis is that the paired mean difference in percent change between eyes is greater than -5%.

$$H_0: \mu_{\text{test}} - \mu_{\text{control}} \leq \delta$$

$$H_a: \mu_{\text{test}} - \mu_{\text{control}} > \delta$$

where...

μ_{test} = ECC percent change in test OVD

μ_{control} = ECC percent change in control OVD

δ = non-inferiority margin: -5%

Success Criteria: If the lower 2-sided 95% confidence interval (equivalent to 1-sided 97.5% CI) for the mean difference between eyes in percent change for ECC is greater than -5%.

If the percent ECC change does not meet normality assumption, a non-parametric test will be performed to evaluate the non-inferiority of ECC endpoint. A similar alpha level of 0.025 and a delta of 5% will be used for the 1-sided non-parametric test.

In addition, ECC for preoperative, 3 months postoperative and the difference between preoperative and 3 months will also be reported as supportive data using the safety population.

6 SECONDARY SAFETY ENDPOINTS

6.1 SERIOUS AND/OR DEVICE-RELATED ADVERSE EVENTS

Serious and/or device related adverse event rates will be tabulated with the frequency and proportion of eyes with these events reported over time and cumulatively by OVD group. The AE rates will be compared to the ISO SPE rate⁴. Comparison of the ISO SPE rates will be performed using an exact test based on the binomial distribution. The null hypothesis is that the study rate for test OVD is equal or lower than the ISO SPE rate, and the alternative hypothesis is that the study rate for test OVD is greater than the ISO SPE rate.

$$H_0: p_t \leq p_i$$

$$H_a: p_t > p_i$$

where

p_t = proportion of test OVD eyes with the AE

p_i = ISO SPE rate with the AE

Success Criteria: If one-sided p-value ≥ 0.025 .

6.2 DISTRIBUTION AND GRADE OF INFLAMMATION

The grades of inflammation (for epithelial and stromal edema, cells and flare, anterior and posterior synechiae, and fibrin presence) will be tabulated with frequency and proportion of eyes with each grading for each event presented over time and cumulatively for both OVD groups.

6.3 RATE OF IOP SPIKES 30 MMHG OR GREATER AT 6 HOURS, 1 DAY, 1 WEEK, 1 MONTH AND 3 MONTHS POSTOPERATIVELY

The rate of IOP spike 30 mmHg or greater at 6 hour, 1 day, 1 week, 1 month and 3 months postoperatively will be tabulated with frequency and proportion by OVD group and analyzed using the McNemar test.

6.4 MEAN CHANGE OF IOP FROM BASELINE

The mean change of IOP at 6 hour, 1 day, 1 week, 1 month and 3 months will be compared to baseline. Descriptive statistics will be presented by OVD group.

7 ADDITIONAL ENDPOINTS

7.1 OCULAR VISUAL SYMPTOMS (NON-DIRECTED)

The ocular visual symptoms (non-directed) will be tabulated with the frequency and proportion of eyes with these events reported over time and cumulatively by OVD group.

7.2 MEDICAL FINDINGS/ADVERSE EVENTS (NON-SERIOUS, NON-DEVICE RELATED)

The medical findings and other adverse events (non-serious, non-device related) will be tabulated with the frequency and proportion of eyes with these events reported over time and cumulatively by OVD group.

7.3 MONOCULAR BEST-CORRECTED VISUAL ACUITY (BCDVA)

The proportion of test OVD eyes achieving 20/40 or better BCDVA will be compared to the ISO SPE rates. The null hypothesis is that the proportion of test OVD eyes achieving 20/40 is greater than or equal to the ISO SPE values and the alternative hypothesis is that the proportion of test OVD eyes achieving 20/40 or better BCDVA is less than the ISO SPE values.

The proportion of eyes achieving each BCDVA acuity line equivalent will also be reported over time by OVD group.

7.4 UNCORRECTED DISTANCE VISUAL ACUITY (UCDVA)

The proportion of eyes achieving each UCDVA acuity line equivalent will be reported over time by OVD group.

8 SAMPLE SIZE CALCULATIONS

Cumulative IOP spikes are defined as an IOP of 30 mm Hg or greater at any visit. The percentage of eyes with IOP spikes will be assumed to be 30% (15798:2001(E), Annex D), and a correlation of 0.5 (medium strength). Using a one-sided, McNemar test and assuming an alpha of 0.025, power = 0.80, and a minimum detectable difference of $\delta=0.10$ yields a sample size of $n=195$ eyes per group. Adding 20% for lost-to-follow-up and screen failures yields a sample size of 241 subjects (482 eyes total with contralateral control).

Assuming a 1-sided, non-inferiority, paired t-test with $\alpha=0.025$, a common standard deviation of 305 cells⁵, and a correlation of 0.50 (medium strength), a sample of $n=195$ subjects (390 eyes) provides over 99% power to detect a minimum clinically significant decrease in mean Endothelial Cell Count (ECC) of at least $\delta =125$ cells. This corresponds to a 5% decrease using a standard deviation of 12% from a baseline ECC of 2500 cells.

Since the sample size required to detect a minimum clinically significant effect for IOP spikes also provides over 99% power to detect a minimum clinically significant effect for ECC loss, the sample size for the study will be based on the number calculated for IOP spikes. Therefore, the sample size required is 195 subjects. Adding 20% for lost-to-follow-up and screen failures yields a sample size of 241 subjects (482 eyes).

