8. STUDY POPULATION

All study subjects will be enrolled from the normal surgical cataract population at up to 10 sites in the USA. Up to 241 subjects will be enrolled to achieve approximately 230 randomized and contralaterally-operated subjects to ensure approximately 200 evaluable subjects at 3 months. Each site should implant a minimum of 20 subjects, and no site may implant more than 25% of the enrollment total.

This study will include only subjects undergoing bilateral, primary, cataract extraction and IOL implantation and who meet all of the study inclusion and exclusion criteria in both eyes. All subjects who meet the inclusion/exclusion criteria will be offered enrollment in the study. Eligibility criteria may not be waived by the investigator. Any questions regarding patient eligibility are to be discussed with AMO prior to subject enrollment. Those subjects who meet the inclusion/exclusion criteria and agree to participate will be randomly assigned to receive the investigational OVD in one eye and

the currently-available, control OVD in the fellow eye. Subjects will be enrolled at each site sequentially until the recruitment goals are met or the site limit is reached.

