The general clinical performance of the bacterially-derived Healon5 OVD is expected to be the same as the currently-available, animal-derived Healon5; however, without the concerns of cross-over contamination. Bacterially-derived Healon5 is designed to create and maintain a deep anterior chamber, which facilitates manipulation inside the eye with reduced trauma to the corneal endothelium and other ocular tissues. It can also be used to efficiently separate and control ocular tissues.

CONCLUSION

The hazards/risks associated with the bacterially-derived Healon5 are acceptable and within those of the currently-available, animal-derived Healon5. The potential clinical benefits of the bacterially-derived Healon5 outweigh the residual risks when the device is used as intended.

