20.2 STUDY ENDPOINTS

Primary Endpoints

SAFETY: CUMULATIVE RATE OF IOP SPIKES 30 MMHG OR GREATER MEASURED POSTOPERATIVELY

The cumulative frequency and proportion of eyes with an IOP spike will be reported for both OVD groups for safety population, PP population and sensitivity analysis. For ITT (with data imputation), only the difference between the OVD groups will be reported. The difference in the cumulative IOP spike rate will be analyzed by the McNemar test using a GLIMMIX procedure taking into account the paired data. The GLIMMIX model will model spike as the dependent variable and OVD group as an independent variable and include the SUBJECT = option for the paired eye data. The hypothesis testing of non-inferiority for cumulative percentage of IOP spikes will be tested using a 1-sided, McNemar test at an alpha of 0.025 with a delta of 0.10 (10%). The null hypothesis is that the paired difference between eyes is less than or equal to -10%. The alternative hypothesis is that the paired difference between eyes is greater than -10%.

$$H_0: p_c - p_t \leq \delta$$

$$H_a: p_c - p_t > \delta$$

where...

p_t = Test rate of IOP spikes 30 mm Hg or greater

p_c = Control rate of IOP spikes 30 mm Hg or greater

δ = non-inferiority margin: -10%

Success Criteria: If the lower 2-sided 95% confidence interval (equivalent to the 1-sided 97.5% CI) for the difference between the proportions is greater than -10%².

EFFECTIVENESS: MEAN PERCENT ECC CHANGE PREOPERATIVELY VS. POSTOPERATIVELY

The mean percent change in ECC from preoperative to 3 months postoperative will be reported by descriptive statistics for both OVD groups for safety population, PP

population and sensitivity analysis. For ITT (with data imputation), only the mean difference between the two OVD groups will be reported. The percent change in ECC from preoperative to postoperative is calculated as followed:

$$\text{Percent change in ECC} = (\text{Postop ECC minus Preop ECC})/\text{Preop ECC}$$

The difference in mean percent change in ECC will be analyzed by a paired t-test. The hypothesis testing of non-inferiority for mean percent ECC change will be tested using a 1-sided, paired t-test at an alpha of 0.025 and a delta of 5%. The null hypothesis is that the paired mean difference for mean percent change in ECC is equal to or less than -5%. The alternative hypothesis is that the paired mean difference in percent change between eyes is greater than -5%.

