5 POSTOPERATIVE PRIMARY ENDPOINTS

5.1 SAFETY: CUMULATIVE RATE OF IOP SPIKES 30 MMHG OR GREATER MEASURED POSTOPERATIVELY

The cumulative frequency and proportion of eyes with an IOP spike will be reported for both OVD groups for the safety population, PP population and sensitivity analysis. For ITT population (with imputation), only the difference between the OVD groups will be reported. The difference in the cumulative IOP spike rate will be analyzed by the McNemar test using a GLIMMIX procedure taking into account the paired data. The GLIMMIX model will model spike as the dependent variable and OVD group as an independent variable and include the SUBJECT = option for the paired eye data. The

hypothesis testing of non-inferiority for cumulative percentage of IOP spikes will be tested using a 1-sided, McNemar test at an alpha of 0.025 with a delta of 0.10 (10%). The null hypothesis is that the paired difference between eyes is less than or equal to -10%. The alternative hypothesis is that the paired difference between eyes is greater than -10%.

$$H_0: p_c - p_t \leq \delta$$

$$H_a: p_c - p_t > \delta$$

where...

p_t = Test rate of IOP spikes 30 mm Hg or greater

p_c = Control rate of IOP spikes 30 mm Hg or greater

δ = non-inferiority margin: -10%

Success Criteria: If the lower 2-sided 95% confidence interval (equivalent to the 1-sided 97.5% CI) for the difference between the proportions is greater than -10%³.

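### Were the 195 pairs for IOP spikes sized for a different test from the planned non-inferiority analysis?

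*SAP*

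**What the plan says.** The sizing paragraph is worded alike in Protocol 20.5 and SAP 8. It defines a cumulative spike as 30 mmHg or more at any visit, takes 30% as the spike rate and 0.5 as the correlation, and continues: "Using a one-sided, McNemar test and assuming an alpha of 0.025, power = 0.80, and a minimum detectable difference of" 0.10, giving 195 eyes per group, that is 195 pairs. SAP 8 then says that "the sample size for the study will be based on the number calculated for IOP spikes".

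The analysis is set out in Protocol 20.2 and SAP 5.1. Protocol 20.2 states: "The hypothesis testing of non-inferiority for cumulative percentage of IOP spikes will be tested using a 1-sided, McNemar test", at alpha 0.025 with a delta of 0.10. In SAP 5.1, "The null hypothesis is that the paired difference between eyes is less than or equal to -10" percent (control minus test), and success is judged by the lower limit of the two-sided 95% confidence interval. The difference is to be "analyzed by the McNemar test using a GLIMMIX procedure taking into account the paired data".

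The ECC paragraph of SAP 8 does name its hypothesis: "Assuming a 1-sided, non-inferiority, paired t-test with" alpha 0.025. Protocol 8 plans for "approximately 230 randomized and contralaterally-operated subjects to ensure approximately 200 evaluable subjects at 3 months". Protocol 17 gives the general expectation: "The general clinical performance of the bacterially-derived Healon5 OVD is expected to be the same as the currently-available, animal-derived Healon5". Neither sizing section states a true IOP difference between the two products.

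**The concern.** The figure 0.10 plays different parts in the two kinds of test. In a test of no difference it is the true effect that one hopes to detect. In a non-inferiority test it is the edge of the null hypothesis, and power depends on a separate assumption about the true difference, usually zero. The phrase about a minimum detectable difference belongs to the first kind, and the planned test is of the second. The ECC paragraph of the same section names non-inferiority, which makes the silence in the IOP sentence stand out.

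The number itself feeds the suspicion: 195 is the smallest number of pairs at which an exact McNemar test of equality reaches 80% power for 40% against 30%. If that was its origin, the 80% describes a test that the trial will not perform, and the power of the primary test is given nowhere. The trial is sized on this one calculation, and SAP 2.5 requires both primary endpoints to succeed, so a real shortfall would matter.

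**Working it through.** **Inputs.** From SAP 8: spike rate 0.30, correlation 0.5, one-sided alpha 0.025, power 0.80, delta 0.10, 195 pairs. From SAP 5.1: margin 10 points, success by the lower 95% limit. From Protocol 8: about 200 evaluable pairs. Assumed, because the sizing text does not give it: a true difference of 0, then 1 point.

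**Discordant pairs.** With marginal rates p1 and p2 and correlation r, the proportion of pairs with a spike in both eyes is p1·p2 + r·√(p1(1−p1)p2(1−p2)). Subtracting this from each marginal rate gives the two discordant cells.

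- 30% and 30%, r = 0.5: 0.09 + 0.5 × 0.21 = 0.195 in both eyes; cells 0.105 and 0.105; discordance 0.21.
- 30% and 40%, r = 0.5: 0.12 + 0.5 × 0.2245 = 0.2322 in both eyes; cells 0.0678 and 0.1678; discordance 0.2355.

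**Where 195 can come from.** (1.960 + 0.8416)² = 7.849.

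1. Exact McNemar test of equality, 40% against 30%: power 79.9% at 194 and 80.1% at 195.
2. Non-inferiority formula using the discordance at the margin plus a continuity correction of 1/delta: 7.849 × 0.2355 / 0.10² = 184.8, and 184.8 + 10 = 194.8, so 195.
3. Wald non-inferiority formula with a true excess of 0.75 points (30.75% against 30%, discordance 0.2115): 7.849 × (0.2115 − 0.0075²) / 0.0925² = 194.0, which is close but not exact.

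The simplest zero-difference formula does not give it: 7.849 × 0.21 / 0.01 = 164.8, so 165 pairs. The documents do not say which route was used.

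**Non-inferiority power at the stated inputs.** The Wald formula at 195 pairs and zero difference gives 0.10 / √(0.21/195) − 1.960 = 3.047 − 1.960 = 1.087, a power of 86.2%. Exact enumeration over all outcomes, with correlation 0.5, gives:

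| Pairs | True excess on test | Wald with continuity correction | Score | Wald |
|---|---|---|---|---|
| 195 | 0 | 82.5% | 84.7% | 85.9% |
| 200 | 0 | 83.8% | 85.8% | 86.8% |
| 195 | 1 point | 73.3% | 76.1% | 77.6% |
| 200 | 1 point | 74.8% | 77.5% | 78.8% |

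At 195 pairs, power is 80% at a true excess of about 0.3, 0.6 and 0.7 points, in the same order of methods.

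**Sensitivity to the correlation.** At 195 pairs and zero difference, correlation 0.45 gives 79.0%, 81.5% and 82.5%, and correlation 0.4 gives 75.5%, 78.5% and 79.2%.

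**Wording side by side.** The sizing sentence and the primary test share the test name, one-sidedness, alpha 0.025, the symbol delta and the size 0.10; SAP 5.1 defines delta as the non-inferiority margin. The ECC paragraph, which is expressly non-inferiority, also speaks of power to detect its delta of 125 cells and equates that to 5%, the ECC margin. So these authors use the language of detection for a margin elsewhere in the same section.

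**The case for a change.** The strongest case for a change is that a shared symbol does not supply the missing assumption. Power in a non-inferiority test moves quickly with the true difference: at 195 pairs it falls to about 73% to 78% at a 1-point excess, and 80% holds only up to an excess of about 0.3 to 0.7 points. Someone reading of 80% power and a detectable difference of 0.10 would not learn this. The exact match of 195 with a 40% against 30% equality test is also hard to ignore, and one sentence of text would settle the matter.

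Part of this stands. The assumed true difference and the variant of the method are not written down, and stating them would be a courtesy to the reader. The rest does not carry. No 40% rate appears in either document, and at least one non-inferiority route also rounds to 195, so no two passages are shown to conflict. The sensitivity to a true excess belongs to any non-inferiority design planned at or near equality. The figures above are benchmarks, too: SAP 5.1 names McNemar through GLIMMIX and not a Wald or score interval, so none of them could be inserted as the power of the planned analysis.

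**Conclusion.** This is missing detail that a statistician fills without difficulty: a paired non-inferiority calculation against the 10-point margin. It is not an inconsistency that calls for a change. At the stated 30% rate and correlation 0.5, and with equal true rates as Protocol 17 leads one to expect, 195 pairs give about 82% to 86% power and 200 pairs about 84% to 87%. On those assumptions the trial is not undersized, and the gap from the stated 80% is on the favourable side.

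That result depends on zero true difference and on the correlation. At correlation 0.4 power at 195 pairs is about 75% to 79%, so the gap from 80% is no larger than the effect of moving this conventional value by 0.1. Writing out the true difference and the method would alter neither the number enrolled, nor the margin, nor the analysis, nor the success rule, which rests on the confidence limit and not on planned power.

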APPENDIX I: TABLE LISTING

| | Test Eye | Control Eye | Comments/ Population |
|---|-----------------|--------------------|---------------------------------|
| ENROLLMENT/PREOP/OP | | | |
| Accountability/Enrollment | | | |
| No. of eyes by OVD model by investigational site | X | X | SF/PP/ITT/Sensitivity |
| Accountability table over time – (No of eyes will be reported for: available for analysis, missing data -discontinued, In interval (no form), missed visit, lost to follow-up, active | X | X | SF/PP/ITT |
| Out of interval subjects listing – No. of eyes | X | X | SF/PP/ITT |
| Demographics | | | |
| Demographic –Age in years (N, Mean, SD, Min., Max), age in groups (<60,60-69,70-79,>=80), race, ethnicity, sex, iris color | | | ITT/SF/PP (By Subject) |
| Age by Site (N, Mean, SD, Min. Max.) | | | SF (By Subject) |
| Other demographic data by site (race, ethnicity, sex) | | | SF (By Subject) |
| Preoperative Characteristics | | | |
| Visual Acuity: No. and percent of eyes for each category | X | X | SF |
| Potential Visual Acuity (≤20/40,>20/40) BCDVA (≤20/30, 20/40, 20/50-20/80, 20/100, >20/100) UCDVA (≤20/40, 20/50-20/80, 20/100, >20/100) | | | |
| Other Preop Items: No. and percent of eyes for each category | X | X | SF |
| Non-clinically significant pathology and/or Medical findings (by finding) | | | |
| Operative Data | | | |
| General Surgical Parameters: No. and percent with each response | X | X | SF |
| IOL model implanted (ZCB00, PCB00, ZKB00, ZLB00, ZMB00) Incision location (Superior, temporal, steep axis, other) Lens placement (Capsular bag, other) Type of Closure (Sutureless, suture) Any concerns/issue with AMO product as part of preparing, performing and/or completing the surgery? (Yes/No) Capsulotomy method (by type) Lens removal method (by method) | | | |
| Surgical Complications: No. and percent with each response | X | X | SF |
| Surgical complications (none, all items listed on CRF, other) Other surgical procedures (none, all items listed on CRF, other) | | | |

| | Test Eye | Control Eye | Comments/ Population |
|--|----------|-------------|-----------------------|
| PRIMARY EFFECTIVENESS ENDPOINTS | | | |
| Cumulative IOP 30mmHg spike rate (95% CI.) between OVD groups | X | X | ITT/Sensitivity/SF/PP |
| Cumulative IOP 30mmHG spike rate (No. and percent) by OVD groups | | | Sensitivity/SF/PP |
| Mean difference between OVD groups in percent ECC change preoperatively vs. 3 months (N, Mean, SD, Median, Min., Max, 95% CI.) | X | X | ITT/Sensitivity/SF/PP |
| Mean percent change of ECC preoperatively vs. 3 months (N, Mean, SD, Median, Min., Max, 95% CI.) by OVD groups | | | Sensitivity/SF/PP |
| SECONDARY SAFETY ENDPOINTS | | | |
| Serious and/or device related adverse event rates (No. and percent) compared to ISO SPE rates | X | X | SF |
| Serious and/or device related adverse event rates over time (No. and percent) | | | |
| Grades of inflammation (No. and percent) over time and cumulatively (epithelial and stromal edema, cells and flare, anterior and posterior synechiae, fibrin presence) | X | X | SF |
| IOP 30mmHG spike rate (No. and percent, 95% CI) between OVD groups at 6 hour, 1 day, 1 week, 1 month and 3 months postoperatively | X | X | SF |
| Change of IOP from baseline at 6-hour, 1-day, 1-week, 1-month, and 3-month postoperatively between OVD groups (N, Mean, SD, Median, Min, Max.) | X | X | SF |
| ADDITIONAL ENDPOINTS | | | |
| Non-directed ocular visual symptoms (No. and percent) over time and cumulatively | X | X | SF |
| Other AE (non-serious, non-device related)/Medical findings (No. and percent) over time and cumulatively | X | X | SF |
| Monocular BCDVA by acuity line over time (No. and percent) | X | X | SF |
| Percent 20/40 or better vs. ISO SPE rate | | | |
| Monocular UCDVA by acuity line at 1 day (No. and percent) | X | X | SF |
| Other IOP/ECC Tables | | | |
| IOP at preoperative, 6 hour, 1 day, 1 week, 1 month and 3 month (N, Mean, SD, Median, Min., Max) | X | X | SF |
| ECC at preoperative, 3 months and difference between preoperatively vs. 3 months (N, Mean, SD, Median, Min., Max) | X | X | SF |
| Other Adverse Event Tables | | | |
| Non-adverse event/procedures (No. and Percent) | X | X | SF |
| Listing of serious and/or device-related Adverse Events by event and by OVD type (include site, age, last reported BCDVA, complications) | X | X | SF |
| | | | |

KEY:OVD=viscoelastic used, VA=Visual acuity, UCDVA=Uncorrected distance visual acuity, BCDVA=Best corrected distance visual acuity, ITT=Intent to Treat, PP=Per protocol, SF=Safety, SD=Standard deviation, Min.=Minimum value, Max.=Maximum value, C.I.=Confidence interval, X=Tables will be provided – blank indicates table will not be generated for that group, 3M=3-month postoperative visit

TIME FRAME: The 3-month postoperative visit is the key timeframe for reporting.

STATISTICS: See text portion of the statistical analysis plan for information on inferential statistics for comparisons between OVD groups
